## Scope of the statistical analysis plan

This SAP is based on the protocol *Efficacy and safety of turoctocog alfa for prophylaxis and treatment of bleeding episodes in previously treated Chinese patients with haemophilia A*

Final protocol version 5 (21-Jul-2017) is based on protocol amendment 3 (and protocol version 1(13 February 2014), protocol version 2 (10 May 2016) and protocol version 3 (19-Aug-2016) including protocol amendment 1 and 2).

The statistical analysis is already pre-specified in the protocol but in order to fulfil a requirement from the Chinese authorities this SAP is written.

## 2 Statistical considerations

Evaluation of data will be based mainly upon descriptive statistics, i.e. summary tables, listings, and figures. Categorical data will be summarised by frequency tables while continuous data will be summarised by mean, standard deviation, minimum and maximum value.

All efficacy endpoints will be reported only for patients without inhibitors (<0.6 BU) and using bleeds with turoctocog alfa treatment. Base on the full analysis set (FAS), but if a patient develops an inhibitor only the time before the positive inhibitor test will be used to evaluate the efficacy endpoints. The following sensitivity analyses will be performed:

- The annualised bleeding rate will be calculated for both treatment-requiring bleeds and non-treatment requiring bleeds
- The annualised bleeding rate will be calculated excluding data from low titer periods
- Treatment success will be summarised excluding data from low titer periods

The main CTR will be written when at least 60 patients have completed the main phase of the trial (completed visit 8 and data is available, including PK data). The patients that have not completed the main phase at the cut off time for the main CTR will also be reported as part of the main phase.

These patients will be included with data until their last scheduled visit prior to the cut-off date. The extension phase data at this time will also be included in the main CTR. The main CTR will present data separately (when relevant) for the above mentioned main and extension phase and this data will also be presented combined.

The primary conclusion will be based on the main CTR and only on the above mentioned main phase data. An updated CTR will be conducted when all patients have completed the extension phase of the trial. The updated CTR will present data separately (when relevant) for the main and extension phase and the combined main and extension phase data. The definition of the main phase will be the same in the main and updated reports. See Figure 16–1.

[figure not shown]

Figure 16-1 in the CTR

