5.3.4 Treatment of bleeding episodes

Bleeds occurring during both the on-demand and in the prophylaxis treatment regimen will be treated with one or more turoctocog alfa i.v. bolus injections. The individual dose is determined by the investigator, using the recommendations in the World Federation of Haemophilia (WFH) guidelines¹⁰.

Dose (IU) = weight (kg) x desired factor level (IU/dl) x 0.5

Example: 50kg x 40IU/dl x 0.5 = 1000 IU of turoctocog alfa

In case of bleeding events, [Table 5-2](#) as well as the WFH guideline¹⁰ may be used to guide dosing. FVIII activity should not fall below the lower range for the given plasma activity level (in % of normal or IU/dl) until the bleeding episode is resolved. As the guidelines are recommendations non-compliance with them will not require protocol deviations. The maximum dose per injection mentioned in this protocol must though be followed.

Table 5–2 Guide for trial product dosing in bleeding episodes¹

Degree of haemorrhage	FVIII level required (%)(IU/dl)	Frequency of doses (hours)/ Duration of therapy (days)
Early haemarthrosis, muscle bleeding or oral bleeding	20-40	Repeat every 12 to 24 hours until the bleeding episode as indicated by pain is resolved or healing achieved
More extensive haemarthrosis, muscle bleeding or haematoma	30-60	Repeat injection every 12 to 24 hours for 3-4 days or more until pain and acute disability are resolved
Life-threatening haemorrhages	60-100	Repeat injection every 8 to 24 hours until threat is resolved

X¹ NovoEight[®] approved summary of turoctocog alfa characteristics

This formula may be used to calculate resulting factor levels:

$IU/dl \text{ (or \% of normal)} = [Total \text{ Dose (IU)}/BW \text{ (kg)}] \times 2 [IU/dl]/[IU/kg]$

Example: $2000 \text{ IU} \times ([2 \text{ IU/dl}]/[IU/kg]) / 70 \text{ kg} = 57 \text{ IU/dl}$

A dose of 2000 IU administered to a 70 kg patient should result in a post-injection FVIII level increase of 57 IU/dl, or 57%.

The patient will be withdrawn from the trial in case he is treated with another FVIII product than turoctocog alfa, see section [6.4](#)

Bleeding treatment should start as soon as a bleed is identified. The investigator should provide the patient in advance the doses needed to treat the bleed of different severities.

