8.2.2 Concomitant medication

A **concomitant medication** is any medication, other than the trial products, which is taken during the trial, including the screening period.

Details of any concomitant medication must be recorded at the first visit. Changes in concomitant medication must be recorded at each visit as they occur.

The information collected for each concomitant medication includes trade name or generic name, indication, start date and stop date or continuing.

If a change is due to an AE, then this must be reported according to section [11](#). If the change influences the patient's eligibility to continue in the trial, the monitor must be informed.

The following concomitant medications are not allowed from visit 2 and during the course of this trial:

- Vitamin K antagonists
- Direct thrombin inhibitors
- Direct factor Xa inhibitors
- FVIII concentrates (other than turoctocog alfa)
- Coagulation factor containing products including PCC, aPCC, whole blood, plasma or cryoprecipitate are allowed in emergency situations for a maximum of 5 administrations. Unrestricted uses of factor containing products is allowed during surgery. See [Table 8-1](#) for washout periods and section [8.5.3.1](#) and [8.5.3.2](#) for necessary laboratory tests
- Use of heparin for a period exceeding 1 month, except for flushing of CVAD

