8.3.1 Bleeding episodes

During the entire trial period all bleeding episodes treated with turoctocog alfa or another haemostatic medication must be entered in the diary, see section [8.6.2](#). Bleeding episodes which do not require treatment can also be entered in the diary

The following will be recorded in the diary for bleeding episodes:

- Date and time of start of bleed
- Date and time of stop of bleed, see [Table 8-4](#)
- Anatomical location of the bleeding episode (Joint, muscle, skin, stomach (gastrointestinal bleeding), mucosal (mouth, gums, nose), urinary system, central nervous system, other)
 - If joint is chosen: knee, ankle, wrist, fingers, elbow, shoulder, hip, toes, jaw
 - If muscle or skin is chosen: arm, leg, hand, buttocks, head/neck, chest, back, stomach, foot
- Anatomical position of body part (left, right)
- Classification of bleed (spontaneous, traumatic, surgical)
- Severity category (mild/moderate or severe), see [Table 8-6](#) Only evaluated by site
- Haemostatic treatment (turoctocog alfa or other treatment to achieve haemostasis)
- Non-medical therapy used
- Clinical evaluation of the haemostasis (Excellent, Good, Moderate or None) – only for bleeds treated with turoctocog alfa, see [Table 8-5](#)

Table 8-4 Definition of stop of bleed

Stop time is:
When the patient/parent or LAR experiences/observes signs of cessation of the active bleed such as; pain relief, no increase in swelling/limitation of motion and improvement in other objective signs of the bleeding episode
Stop time is not:
When pain and objective signs of the bleeding episode are completely resolved

Table 8–5 Definition of haemostatic response

Category	Definition
Excellent	abrupt pain relief and/or unequivocal improvement in objective signs of bleeding within approximately 8 hours after a single injection
Good	definite pain relief and/or improvement in signs of bleeding within approximately 8 hours after an injection, but possibly requiring more than one injection for complete resolution
Moderate	probable or slight beneficial effect within approximately 8 hours after the first injection; usually requiring more than one injection
None	no improvement, or worsening of symptoms within approximately 8 hours after the first injection; usually requiring more than one injection

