8.5.3.2 HIV

Blood samples for HIV testing is sampled at visit 1, visit 8, end of trial visit and if applicable at an unscheduled visit.

- HIV 1
- HIV 2
- HIV viral load

If the patient has a previous positive HIV result or a HIV test that has been performed within 6 months, the result can be transcribed into the eCRF and the above test do not need to be performed.

In case the patient is HIV positive, the result of the viral load must be used for the assessment of an exclusion criterion, see section [6.3](#).

If the patient has during the trial been injected with a product that may contain any risk of HIV infection a test for HIV must be performed before the next injection of trial product. If a local test for hepatitis has been performed before injection of the product this must be recorded in the eCRF.

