17.4 Data handling

If the patient is withdrawn from the trial or lost to follow up, then the patient's data will be handled as follows:

- Data already collected and data collected at the end-of-trial visit will be retained by Novo Nordisk, entered into the database and used for the trial report.
- Safety events will be reported to Novo Nordisk and regulatory authorities according to local/national requirements.

If data is used, it will always be in accordance with local regulations and IRBs/IECs.

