### **Efficacy endpoints**

The primary endpoint will be repeated for the extension phase and the combined main and extension phase (total trial period of 24 months) . The analysis is similar to the primary analysis

Number of bleeds (total bleeds assessed as annual bleeding rate) per patient during both the main phase of 6 months and the trial period of 24 months. This endpoint will only be presented for patients on prophylaxis regimen and will be reported using only treatment requiring bleeds. The following sensitivity analyses will be performed:

- The annualised bleeding rate will be calculated for both treatment-requiring bleeds and non-treatment requiring bleeds
- The annualised bleeding rate will be calculated excluding data from low titer periods

The annualised bleeding rate will be analysed by a negative binomial model and estimated annualised bleeding rate with confidence interval will be presented by trial phase and treatment regimen. As a sensitivity analysis, a Poisson model with over-dispersion will also be applied. Analyses and presentations will be made for the preventative regimen by age groups, trial phase and total.

When turoctocog alfa is administered via a butterfly, the dead space is subtracted from the total volume of the dose to account for the compound left in the butterfly device after injection.

- Consumption of turoctocog alfa for bleeding treatment (average dose to treat a bleed, number of injections and IU/kg per bleed) during both the main phase of 6 months and the trial period of 24 months

This endpoint will be summarised and listed. The presentations will be made by age groups, type of regimen, trial phase and total.

- Consumption of turoctocog alfa during prophylaxis treatment (average prophylaxis dose, number of injections and IU/kg per month and per year) per patient during both the main of 6 months and the trial period of 24 months

This endpoint will be summarised and listed. The presentation will be made for the preventative regimen by trial phase, age groups and total.

- Total consumption of turoctocog alfa (IU/kg per month and per year) per patient during both the main phase of 6 months and the trial period of 24 months. This endpoint will be summarised and listed. The presentation will be made by type of regimen, trial phase, age groups and total

- Surgery-related endpoints where applicable:

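### As written, the main bleeding rate omits prophylaxis bleeds treated only with another haemostatic product but keeps the follow-up time, so it is biased slightly downward

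*SAP*

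**What the plan says.** SAP section 2, with the same text in protocol section 16, sets a general filter: "All efficacy endpoints will be reported only for patients without inhibitors (<0.6 BU) and using bleeds with turoctocog alfa treatment". Under Efficacy endpoints, the SAP adds that the bleeding rate is presented for prophylaxis patients only and "will be reported using only treatment requiring bleeds". That paragraph names no product, and the plan does not define when a bleed counts as requiring treatment. One sensitivity analysis widens the count: "The annualised bleeding rate will be calculated for both treatment-requiring bleeds and non-treatment requiring bleeds".

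The protocol foresees treatment with other products. Section 8.2.2 says that PCC, aPCC, "whole blood, plasma or cryoprecipitate are allowed in emergency situations for a maximum of 5 administrations". Section 8.3.1 requires diary entry of bleeds treated with either turoctocog alfa or another haemostatic medication, and the diary has a field for this: "Haemostatic treatment (turoctocog alfa or other treatment to achieve haemostasis". Section 8.5.3.2 shows that a patient may carry on after a product with an infection risk, since "a test for HIV must be performed before the next injection of trial product". A different rule applies to other FVIII products: under section 5.3.4 the patient is "withdrawn from the trial in case he is treated with another FVIII product than turoctocog alfa". Section 17.4 nevertheless keeps such a patient's data, which are "entered into the database and used for the trial report".

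**The concern.** An annualised bleeding rate on prophylaxis should count the bleeds that broke through, divided by the time at risk. Which product stopped a bleed has no bearing on whether prophylaxis failed to prevent it. The product filter makes sense for haemostatic response, where only a turoctocog alfa-treated bleed can be rated, and for the dose used per bleed. Carried over to the bleeding rate, it removes real breakthrough bleeds from the numerator and leaves the denominator alone. The only cut to follow-up time in the plan is at a positive inhibitor test; treatment with another product does not shorten it.

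The error can go only one way, towards a lower rate. The trial has no control arm and its evaluation is mainly descriptive, so the rate is read as it stands and no comparison group carries the same error.

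**Working it through.** **Which bleeds count.** Applying the two rules together, as their wording asks, gives:

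| Treatment of the bleed (prophylaxis patient, before any inhibitor) | Main bleeding rate | All-bleeds sensitivity rate | Patient's time counted |
|---|---|---|---|
| Turoctocog alfa only | in | in | yes |
| Turoctocog alfa and another product | in | in | yes |
| Another product only | **out** | probably in | yes |
| None needed | out | in | yes |

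The third row is the problem. The all-bleeds analysis must drop the product filter to make sense, because untreated bleeds had no turoctocog alfa. It therefore probably takes in the third row too, but it adds the fourth row at the same time. The difference between the two rates does not show the third row alone.

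**Can the third row occur?** Yes, by two routes. The first is an emergency factor-containing product under section 8.2.2, after which the patient may continue. The second is a prohibited FVIII concentrate. That leads to withdrawal (sections 5.3.4 and 6.4), but the data and time up to then stay in the report (section 17.4).

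**Size.** The documents state no bleeding rate and no expected number of such bleeds, so there is no planned figure to reproduce. The effect per omitted bleed can be computed.

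Inputs:
- Prophylaxis patients: 22 to 53 (protocol Table 6–1).
- Main-phase treatment time: visit 2 to visit 8 is 14 + 5 × 28 = 154 days (flow chart and section 8.1.3), or 154/365.25 = 0.42 years. The upper value is the nominal 6 months, 0.5 years.

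Formula: fall in the pooled rate = k / (n × T), where k is the number of omitted bleeds, n the number of patients and T the years per patient.

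- Shortest exposure: 22 × 154/365.25 = 9.28 patient-years, so one bleed gives 1/9.28 = 0.108 per year.
- Longest exposure: 53 × 0.5 = 26.5 patient-years, so one bleed gives 1/26.5 = 0.038 per year.
- Five omitted bleeds: 5/9.28 = 0.54 and 5/26.5 = 0.19 per year.
- For the patient concerned: 1/0.42 = about 2.4 per year.
- 24 months, assuming all stay on prophylaxis: 22 × 2 = 44 to 53 × 2 = 106 patient-years, so 0.023 to 0.009 per year per bleed.

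Relative size for one bleed over 154 days, at assumed true rates of 2 and 6 per year:

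| True rate (assumed) | n | Expected bleeds | Reported rate | Change |
|---|---|---|---|---|
| 2 | 22 | 18.6 | 1.89 | −5.4% |
| 2 | 53 | 44.7 | 1.96 | −2.2% |
| 6 | 22 | 55.7 | 5.89 | −1.8% |
| 6 | 53 | 134.1 | 5.96 | −0.7% |

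These are crude pooled rates. When follow-up is similar across patients, the negative binomial estimate for a single group is close to them.

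**The case against.** The case for leaving the text alone is that the situation is narrow. Other FVIII concentrates are prohibited. Outside surgery, the other factor-containing products are for emergencies and capped. Trial product is dispensed to cover need until the next visit (section 8.6.3). Bleeding during an operation is not a bleeding episode under Table 8–7. The rate is a supportive secondary endpoint, and the all-bleeds analysis probably includes the omitted bleeds. All of this stands, and it is why the effect is expected to be small. It does not justify a rule that drops a breakthrough bleed because of the product used, when the correction costs almost nothing.

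Two stronger readings are tempting, and the documents support neither.

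First, a reader might infer that the general rule and the bleeding-rate paragraph contradict each other, so that two programmers would get different main rates. The general rule covers all efficacy endpoints, and the later paragraph narrows the count further. Read literally they are two filters applied together, with a definite result. It is fair to say that precedence is not spelled out and that the endpoint's description as total bleeds suggests a wider intention. But the fault lies in what the rule does, more than in a clash between rules.

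Second, a reader might infer that treatment success is inflated by bleeds given both turoctocog alfa and another factor-containing product, and that a worst-case analysis counting them as failures is needed. Table 8–5 ties the two lower ratings to the first 8 hours or so after the first injection and the top rating to a single injection, and the investigator reviews each rating with the patient (section 8.3.1). A gap remains, since 'good' may follow a later injection and no category mentions other products. But the other product may have been given before turoctocog alfa was at hand, so scoring every such bleed as failure would be debatable. No success threshold is stated for it to overturn.

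**Conclusion.** The point holds for the bleeding rate. Under the rules as written, a prophylaxis bleed treated only with another haemostatic product is missing from the main annualised bleeding rate while the patient's time is counted, and the bias is downward. The size is about 0.04 to 0.11 per year for each omitted bleed in the main phase and 0.01 to 0.02 over 24 months. This rests on the planned 22 to 53 prophylaxis patients, scheduled visit timing or the nominal 6 months and, for the longer period, no switch of regimen. The number of such bleeds is unknown and is probably low.

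The relative effect could be larger in the planned summaries by severity and site, because emergency products may cluster in severe bleeds. That is an inference; the documents do not state it. No conclusion about efficacy is shown to change. The point does not extend to a finding against the primary endpoint.

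**What to change.** In the SAP:

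1. State that the annualised bleeding rate counts every treatment-requiring bleed, meaning a bleed treated with any haemostatic product.
2. Limit the turoctocog alfa restriction to haemostatic response and consumption for bleed treatment. Leave the cut-off at a positive inhibitor test as it is.

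Protocol section 16 carries the same text and SAP section 3 declares no changes, so the clarification should be recorded in section 3. The cost is two sentences. Bleeds treated with another product must already be entered in the diary, so no new data are needed. The downside for the sponsor is that the rate may come out slightly less favourable.

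Optional: list the bleeds that received another factor-containing product, with product, dates, severity and any rating, so that readers can see how many rated bleeds were co-treated. The diary field as described separates turoctocog alfa from other treatment but does not identify factor-containing products. The listing would need each bleed linked to the concomitant-medication record, which holds product name, indication and dates (section 8.2.2). A worst-case failure analysis is not required.

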### Sample size calculation

No formal sample size calculations have been performed. A sample size of 60 patients is considered a sufficient number of patients to evaluate safety and efficacy of turoctocog alfa. The results of this study will supplement results from a corresponding study in non -Chinese patients.

### Definition of analysis sets

All main descriptions and analyses of safety and efficacy data will be based on the FAS, as defined in ICH E9 Guidelines (Statistical Principles for Clinical Trials). The FAS includes all dosed patients with data after dosing.

The ABR will also be summarised by the following subgroups:

Cause of bleed (Spontaneous, Traumatic, Re-bleed), Site of bleeding (Central nervous system, Haemarthrosis (Joint), Gastrointestinal, Subcutaneous, Muscular or other), Classification of bleeding (Mild/Moderate or Severe)

### Handling of exceptional pharmacokinetic outlier data

Exceptional outlier PK profiles and/or individual plasma concentrations may be excluded when analysing PK endpoints based on the FAS. If exceptional outlier data are identified, a sensitivity analysis including the outlier data will be conducted.

Unless otherwise stated, analysis results obtained from FAS excluding exceptional outliers will be presented with reference to the “full analysis set excluding outliers”. The results of the sensitivity analysis including the exceptional outliers will refer to “full analysis set incl. all data”.

### **Documentation of analysis sets**

The decision to exclude data points from analysis of PK endpoints based on the FAS will be made from a review prior to database lock. It will be the joint responsibility of the clinical pharmacology scientist and the trial statistician.

The profiles or observations to be excluded from the FAS and the reason for their exclusion will be documented and signed by the clinical pharmacology scientist and the trial statistician as part of the database lock minutes. The documentation will be stored together with the remaining trial documentation. This will also be described in the CTR.

### **Primary endpoint**

Haemostatic effect of turoctocog alfa when used for treatment of bleeds, assessed on a four point scale for haemostatic response (excellent, good, moderate and none) during the main phase (6 months duration per patient).

In addition treatment success will be summarised by counting haemostatic responses rated as good or excellent as success and responses rated as moderate and none as failure. If the haemostatic response is missing, the response will be counted as failure in the primary analysis, but a sensitivity analysis will be performed excluding bleeding episodes with missing response. Treatment success will also be summarised excluding data from low titer periods as a sensitivity analysis to the primary analysis.

The haemostatic effect of turoctocog alfa will also be summarised by the following subgroups:

Cause of bleed (Spontaneous, Traumatic, Re-bleed), Site of bleeding (Central nervous system, Haemarthrosis (Joint), Gastrointestinal, Subcutaneous, Muscular or other), Classification of bleeding (Mild/Moderate or Severe)

Analyses and presentations will be made by age groups, type of regimen, trial phase and total.

